The chemical precursor for [¹⁸F]FLT is provided by ABX in single-use, 10 mg vials that are delivered to the custody of [name], the lead radiochemist for this project. They are stored in a controlled temperature refrigerator in a locked and secure room and they are inventoried with a chain of custody maintained from the time of receipt. Each radiosynthesis is done by [name], [name] or their designee and, after passing all required quality control assays, the product [¹⁸F]FLT dose is drawn up under the authority of the nuclear medicine physician co-investigator, [name], [name] or their designee. The quality control tests that must be passed prior to release of the product [¹⁸F]FLT for injection include the pH, radioactive purity, radiochemical purity, specific activity, sterilizing filter integrity, tests for Kryptofix [2.2.2], acetonitrile, acetone, dimethylsulfoxide, endotoxins and particulates. Acceptance criteria are detailed in the CMC section of this IND. The [¹⁸F]FLT dose is drawn up into a syringe, assayed for mCi at time of injection, labeled and passed to the physician investigator who oversees the re-assay of the dose and the administration to the research subject.

6.iii.10. CORRELATIVE / SPECIAL STUDIES

Study data are comprised of imaging parameters from at least two and as many as four [¹⁸F]FLT PET studies.

6.iii.10.a. [¹⁸F]FLT PET/CT Image Analysis

Preliminary data suggests that [¹⁸F]FLT is essentially irreversibly phosphorylated and trapped inside cells during the imaging period. Prior to this point, however, there is a flux of unphosphorylated [¹⁸F]FLT (reversible component). If the rate of phosphorylation (k_3) is low, then the early contribution of perfusion to the measured tumor activity is high. Assuming the phosphorylation rate correlates to the proliferative rate, a high rate of phosphorylation means that the cumulative measured tumor activity should be representative of cellular proliferation.

Volumes of interest (VOIs) will be drawn around the target lesions on the [¹⁸F]FLT images based on the tumor localization on the baseline CT. [¹⁸F]FLT PET studies will be registered based on their corresponding CT transmission scans images, and time activity curves (TACs) will be calculated.

[figure not shown]

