Abbreviations: RANO, Response Assessment in Neuro-Oncology; CR, complete response; PR, partial response; SD, stable disease; PD, progressive disease; FLAIR, fluid-attenuated inversion recovery; NA, not applicable
* Progression occurs when this criterion is present.
Δ Increase in corticosteroids alone will not be taken into account in determining progression in the absence of persistent clinical deterioration.

The primary analysis variables for the study are:

- Percentage change in K_1 , FLT flux and SUV for [¹⁸F]FLT PET/CT
- Assessment of clinical response per the response criteria listed above.
- Survival

Secondary analysis variables are:

- Heterogeneity in K_1 , FLT flux and SUV for [¹⁸F]FLT PET/CT at baseline.
- Comparison of heterogeneity at different times

6.iii.13. DATA REPORTING / REGULATORY CONSIDERATIONS

Adverse event lists, guidelines, and instructions for AE reporting are described in Section 6.iii.8. The Principal Physician Investigator is responsible for maintaining complete and timely, HIPAA-compliant electronic records of clinical and image datasets.

6.iii.14. STATISTICAL CONSIDERATIONS

6.iii.14.a. Study Description

This is a study involving [¹⁸F]FLT PET/CT imaging of patients with brain tumors at different times during the course of standard treatment. Thirty patients with brain tumors and who are planning standard therapy with surgical resection, chemotherapy or radiotherapy or any combination, will be enrolled. We will evaluate the values for percentage changes in [¹⁸F]FLT PET measures observed following 1-3 weeks of therapy, shortly after finishing therapy and at time of

recurrence or at one year, whichever comes first and explore associations between [¹⁸F]FLT PET parameters and their changes and clinical outcome.

6.iii.14.b. Power Calculations

For hypotheses 2 and 3, we will use patient survival as our outcome variable and the analysis will be based on the Cox proportional hazards model with adjustment for confounding. We have estimated that with 30 patients our study will have power characteristics presented in Table 6.iii.7. These calculations used a value for the study effect of 0.75.

Table 6.iii.7. Power calculation for measuring response	FU=2 yrs	FU=7 yrs
Power without cofounders	0.79	0.80
Power using cofounders, including FDG PET/CT	0.87	0.83
Effect of 15% measurement error	0.89	0.84

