The analysis of data for these hypotheses involves within-subject changes where the variance in values will be less than between-subject FLT results that we have published. Furthermore, this power analysis has assumed that only data from a single volume of interest (VOI) for each subject will be used. In the context of our aims, this could be considered inefficient. In many subjects it will be possible to include data from spatially well-separated and hence substantially uncorrelated sub-regions within large tumors (Spence, 1998) as distinct sampling units for consideration with this hypothesis. Notwithstanding the additional variability that sub-region measurements will have, it is likely that some gains in statistical precision can be realized by this approach. Thus the 90% power estimate is conservative.

Hypothesis 1. Among GBM patients identified as progressing according to Macdonald criteria at 1-month follow-up, the mean FLT flux in true progression cases will be compared to the corresponding mean in the pseudo-progression cases. Preliminary data indicate that 40% of MRI diagnosed progression can be expected to be pseudo-progression. Our data on recurrence vs radionecrosis for KFLT recurrences showed a mean of 0.017 and a standard deviation of 0.005 (Spence, 2006). The mean of the radionecrosis group was 0.004, roughly one-quarter for that for recurrences. Thus, conservatively, assuming that pseudo-progressors showed even a 30% increase over the mean KFLT value, the expected difference between the groups would be 0.017×0.3 or about 0.005. From this, the expected standardized effect is 0.99. Using a 2-sample t-test with significance level of 5% for assessment of the hypothesis, the power of our study is about 95%.

6.iii.14.c. Analysis Plan

Percentage change between pre-treatment and post-therapy measurements will be computed for [¹⁸F]FLT PET/CT measures of transport, K₁, and flux (KFLT). Log transformations will be considered if the rates of change are highly skewed. Outcome analysis studies are directed toward predicting tumor response. In the case of progression, a multivariate logistic regression will be used to produce an analysis of how the combination of standard diagnostics plus the FLT parameters (K₁, KFLT, SUVmean) obtained shortly after therapy can best be combined to

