obtain a prognostic variable for determination of progression. Although the prognostic variable will provide a direct assessment of the probability of response for an individual patient, we will also develop a ROC characterization of its diagnostic performance. We fully appreciate that the small number of patients means that this analysis may suffer from a lack of power but it should be useful in planning a larger follow-up if the results are encouraging.

A similar approach will be used for survival analysis.. Here we will use multivariate Cox regression analysis with both baseline and follow-up variables to be considered.

The heterogeneity of the within-tumor proliferation obtained by application of the elliptical heterogeneity measure developed by Eary et al (2008) will be used in a secondary analysis.

6.iii.14.d. Stratification Factors

Not Applicable.

6.iii.14.e. Reporting and Exclusions

Evaluation of Toxicity: All patients will be evaluable for toxicity from their [¹⁸F]FLT PET.

6.iii.15. LITERATURE CITED

Carlson RW. Sequencing of endocrine therapies in breast cancer--integration of recent data. *Breast Cancer Res Treat* 2002; 75 Suppl 1 S27-32; discussion S33-5.

Carlson RW, Allred DC, Anderson BO, Burstein HJ, Carter WB, Edge SB, Erban JK, Farrar WB, Goldstein LJ, Gradishar WJ, Hayes DF, Hudis CA, Jahanzeb M, Kiel K,

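### Tumor sub-regions offered as extra sampling units for the Cox hypotheses add no independent survival outcomes and should not support the claim that power is conservative (minor)

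*Combined protocol and SAP*

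**What the plan says.** For Hypotheses 2 and 3, section 6.iii.14.b of the combined protocol and SAP states: "we will use patient survival as our outcome variable and the analysis will be based on the Cox proportional hazards model". The sample size is 30 patients. The next paragraph, still on these hypotheses, says the power calculation assumed that "only data from a single volume of interest (VOI) for each subject will be used" and calls this possibly inefficient. It then says that in many subjects the data could include "spatially well-separated and hence substantially uncorrelated sub-regions within large tumors", treated "as distinct sampling units for consideration with this hypothesis". It grants that sub-region measurements are more variable, but expects that "it is likely that some gains in statistical precision can be realized by this approach", and ends: "Thus the 90% power estimate is conservative". The other reason given for this conclusion is that within-subject changes vary less than between-subject values.

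Section 6.iii.10.a describes the planned measurement: "Volumes of interest (VOIs) will be drawn around the target lesions". Section 6.iii.14.c does not mention sub-region rows, clustering or a patient-level summary of several sub-regions. Its description of the logistic model, which the survival analysis is to follow in a similar way, refers to a "direct assessment of the probability of response for an individual patient".

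**The concern.** A patient contributes one survival time however many parts of the tumor are measured. Three sub-regions entered as three rows repeat the same death or censoring three times. If the software treats those rows as independent, the standard error is too small whenever sub-regions of one patient resemble each other. P-values are then too small and confidence intervals too narrow. The Schema (6.iii.1) says promising data will be used to design larger trials, so false precision could carry forward. Separately, extra sampling units are not a sound reason for calling the power conservative, because power in a Cox model depends on the number of patients who die.

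**Working it through.** **Inputs from the documents.** One survival time per patient, Cox model, 30 patients, and the 2-year follow-up column of Table 6.iii.7. A 5% level is stated only for the Hypothesis 1 t-test; a two-sided 5% level is assumed here for the Cox test.

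**Assumed, because the documents give no figure.** m = 2 to 4 sub-regions per patient, within-patient correlation ρ = 0 to 0.5, and exponential survival with median 1.25 years. Expected deaths by 2 years are 30 × (1 − 0.5^(2/1.25)) = 30 × 0.67, or about 20. Three rows per patient would appear as 90 rows and about 60 deaths, but only about 20 deaths are independent.

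**The plan's own figure.** The 90% cannot be reproduced. The number of events, the Cox significance level, the covariate distribution and the scale of the 0.75 effect are not stated, and the table itself runs from 0.79 to 0.89. Of the readings tried, only a log hazard ratio of 0.75 per SD reaches such values. There power = Φ(0.75√D − 1.96), giving Φ(0.85) = 0.80 at D = 14 and Φ(1.31), about 0.90, at D = 19. The formula is used here only to show that D counts patient deaths, at most 30, and sub-region rows do not raise it.

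**Effect of treating rows as independent.** With m rows in every patient, the row-level Cox score at zero effect is m times the score from the patient means (Breslow ties). A patient mean has variance σ²[1 + (m − 1)ρ]/m. The true variance of the row score is therefore about m²·D·σ²[1 + (m − 1)ρ]/m = mDσ²[1 + (m − 1)ρ], while the model uses mDσ². The ratio is DE = 1 + (m − 1)ρ, and the actual rejection rate is 2[1 − Φ(1.96/√DE)]. For m = 3 and ρ = 0.3, DE = 1.6, 1.96/1.265 = 1.55, and the rate is 12.1%.

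The exact score identity needs equal m, whereas the plan has only some patients in mind. For unequal m, the same variance argument gives DE = Σmᵢ[1 + (mᵢ − 1)ρ]/Σmᵢ. With 15 patients at three rows and 15 at one, DE = (45(1 + 2ρ) + 15)/60 = 1 + 1.5ρ.

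Rejection rate of a nominal 5% test, rows taken as independent:

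| Rows | ρ = 0 | 0.1 | 0.3 | 0.5 |
|---|---|---|---|---|
| 2 in all, formula | 5.0% | 6.2% | 8.6% | 11.0% |
| 3 in all, formula | 5.0% | 7.4% | 12.1% | 16.6% |
| 3 in all, simulation | 4.8% | 7.5% | 12.0% | 16.9% |
| 4 in all, formula | 5.0% | 8.6% | 15.5% | 21.5% |
| 3 in half, 1 in half, formula | 5.0% | 6.8% | 10.4% | 13.8% |
| 3 in half, 1 in half, simulation | 5.4% | 6.1% | 9.4% | 13.6% |

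With three sub-regions averaged to one value per patient, the simulated rate is 4.6-6.0%.

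**The valid gain.** Averaging can help, but its size depends on the model. Take three sub-regions, ρ = 0.1 and an assumed log hazard ratio of 0.75 per SD:

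- If survival follows a patient-level value that each sub-region measures with noise, power is 0.13 for one sub-region, 0.27 for the patient mean and 0.31 for rows taken as independent.
- If survival follows the tumor average itself, the figures are 0.41, 0.85 and 0.85.

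These results only show the dependence on the model; neither is an estimate for this trial. If the single volume in the power calculation is already the whole lesion, as 6.iii.10.a suggests, much of the averaging is already in it.

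**The case against.** The strongest reply is that the plan does not commit to this analysis. The sentence is hedged, applies to many subjects rather than all, and is not carried into 6.iii.14.c, whose wording points to the individual patient. That stands. A reader might infer that the Cox results will have inflated error, or that the plan specifies rows analysed as independent. The documents do not say so; that step is an inference from the phrase about sampling units.

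A second reply is that under the plan's own premise of substantially uncorrelated sub-regions there is little or no inflation. That also stands at ρ = 0, and the excess at ρ = 0.1 is small. But no figure supports the premise. The 1998 source cited for it is missing from the literature list, though other cited works are missing too, so this looks clerical and carries little weight.

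A third reply is that the plan claims only some gain in precision, not extra deaths, and that patient-level averaging can deliver one. This is right as far as it goes. It supports a claim about noise in the covariate, not one about additional sampling units.

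A reader might also infer that Table 6.iii.7 is overstated for this reason. It is not: the calculation assumed one volume per subject.

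**Conclusion.** The point holds as a minor one. Sub-regions cannot act as independent sampling units for a survival outcome measured once per patient, and an expected gain from counting them that way should not support conservative power. If rows were analysed as independent with three sub-regions, a 5% test would reject about 7 / 12 / 17% of the time at correlations of 0.1 / 0.3 / 0.5 when every patient has three, and about 6 / 9-10 / 13-14% when half do. It would stay near 5% if sub-regions were uncorrelated. The figures rest on assumed correlations and numbers of sub-regions; the simulated ones also assume a 1.25-year median survival and 2-year follow-up.

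The documents do not support attributing any power loss or gain to the protocol on this ground, because the size of the averaging benefit depends on an unstated model and on what the single volume covers. The other reason given for conservative power, lower within-subject variance, is not examined here.

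**What to change.** In 6.iii.14.b, replace the sentence on sampling units with a statement that the patient is the unit of analysis for the Cox models. Each FLT parameter then enters as one value per scan per patient, from the whole-tumor volume or, for K1, KFLT and SUV, the mean of its sub-regions. State whether the single volume assumed for Table 6.iii.7 is the whole lesion. Limit any precision claim to noise reduction from patient-level averaging, and do not cite extra sampling units in support of conservative power. Label any analysis of sub-region rows exploratory and give it a patient-clustered variance. That variance can itself be somewhat liberal with 30 patients: 5.2-6.5% in simulation with a small-sample correction, 6.6-8.6% without.

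The cost is a few sentences, with no new data or scans. Intervals become wider only if rows would otherwise have been analysed as independent.

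### The 90% power stated for Hypotheses 2 and 3 exceeds every cell of Table 6.iii.7, and two of the table's three rows lose power as follow-up lengthens

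*Combined protocol and SAP*

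**What the plan says.** Section 6.iii.14.b makes survival the outcome for Hypotheses 2 and 3 and states that "the analysis will be based on the Cox proportional hazards model with adjustment for confounding". It then says that "with 30 patients our study will have power characteristics presented in Table 6.iii.7", and adds: "These calculations used a value for the study effect of 0.75". The table as printed is:

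| Row | Follow-up 2 years | Follow-up 7 years |
|---|---|---|
| 1. Unadjusted | 0.79 | 0.80 |
| 2. "Power using cofounders, including FDG PET/CT" | 0.87 | 0.83 |
| 3. "Effect of 15% measurement error" | 0.89 | 0.84 |

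The text after the table gives two reasons why power may be better than tabulated. Variation within a patient should be smaller than the published variation between patients. Also, "this power analysis has assumed that only data from a single volume of interest (VOI) for each subject will be used", whereas separate sub-regions of large tumours could be used "as distinct sampling units for consideration with this hypothesis". The paragraph ends: "Thus the 90% power estimate is conservative".

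**The concern.** There are two problems. First, the text treats 90% as an established estimate, but none of the six cells is that high. The section's only other power figure, about 95%, belongs to the t-test for Hypothesis 1.

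Second, the columns differ only in length of follow-up. With the same 30 patients, the same effect and proportional hazards, deaths can only accumulate, so power should not fall. It falls in rows 2 and 3 and rises by one point in row 1, and no reason is given. A smaller oddity is that the measurement-error row lies 1 to 2 points above the row without error, where a loss would be expected.

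These are the only power figures for Hypotheses 2 and 3, and survival is listed among the primary analysis variables in section 6.iii.12. A reader who accepts the sentence would set a null survival result against a false-negative risk of at most 10%. The adjusted row implies 13% at 2 years and 17% at 7 years. The results are also meant to inform larger trials.

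**Working it through.** **The plan's own figures.** The cells cannot be reproduced, because the scale of the 0.75 effect, the alpha for the Cox analysis and the expected deaths are not given. With all 30 patients counted as deaths and two-sided 5%, a log hazard ratio of 0.75 per SD gives power 0.98, a hazard ratio of 0.75 per SD gives 0.35, two equal groups with log hazard ratio 0.75 give 0.54, and two equal groups with hazard ratio 0.75 give 0.12. None matches a cell. The checks below therefore compare the cells with each other.

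**Stated 90% against the cells.** The shortfall from 0.90 at 2 and 7 years is 0.11 and 0.10 in row 1, 0.03 and 0.07 in row 2, and 0.01 and 0.06 in row 3.

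**Information implied by each cell.** At two-sided 5% (assumed; the plan states 5% only for Hypothesis 1), information is proportional to (1.96 + z_power)². For row 2 at 2 years this is (1.96 + 1.126)² = 9.53. At 7 years it is (1.96 + 0.954)² = 8.49.

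| Row | 2 years | 7 years | Ratio 7:2 | Range allowing for two-decimal rounding |
|---|---|---|---|---|
| 1 | 7.65 | 7.85 | 1.03 | 1.00–1.05 |
| 2 | 9.53 | 8.49 | 0.89 | 0.87–0.92 |
| 3 | 10.15 | 8.73 | 0.86 | 0.83–0.89 |

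The ratios for rows 2 and 3 stay below 1 at one-sided 5% (0.88 and 0.85) and at two-sided 1% (0.91 and 0.88). If 0.75 were a log hazard ratio per SD, dividing by 0.75² would give about 16.9 deaths at 2 years and 15.1 at 7 years for row 2.

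**Direction of change under the stated model.** Cox analyses were simulated with assumed inputs: 30 patients followed 2 or 7 years, log hazard ratio 0.75 per SD, baseline median survival from 0.3 to 3 years, three confounder settings and frailty variance 0 or 0.5. That makes 36 scenarios of 4,000 runs. Adjusted power never fell from 2 to 7 years; the change was +0.3 to +22.6 points. With medians of 0.3 to 0.5 years the rise was only +0.3 to +3.0 points. Measurement error of 0.15 SD lowered power by 0.2 to 2.3 points.

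**Transposed headers.** The ratios would become 0.97, 1.12 and 1.16. Only row 1 would then fall, by one point, so this explanation cannot be excluded.

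**Simulation noise.** If the cells came from independent simulations, the falls in rows 2 and 3 are 2.5 and 3.3 standard errors at 1,000 runs per cell, but only 1.1 and 1.5 at 200 runs. The row 1 change is 0.55 standard errors at 1,000 runs. Row 3 exceeds row 2 by 1.4 and 0.6 standard errors at 1,000 runs, so that oddity may be noise or a mislabelled row.

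**Distance from 90%.** Power of 0.90 needs information of 10.51. For the adjusted analysis at 7 years:

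| Reading of the table | Power | Extra information needed |
|---|---|---|
| As printed | 0.83 | 10.51/8.49 − 1 = 24% |
| Rows 2 and 3 swapped | 0.84 | 10.51/8.73 − 1 = 20% |
| Headers transposed | 0.87 | 10.51/9.53 − 1 = 10% |
| Both | 0.89 | 10.51/10.15 − 1 = 3.5% |

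The implied false-negative risk runs from 11% to 17%.

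**The case against.** The strongest reply is that the word conservative rests on the two arguments after the table and not on the table alone. The sub-region argument has substance. In simulation (7 years, median survival 1.25 years, assumed noise), averaging three regions per patient instead of using one raised power from 0.83 to 0.89 with noise of 0.5 SD, and from 0.58 to 0.80 with noise of 1 SD. These are information gains of about 1.20 and 1.68. Applied to the adjusted cells, they would lift 0.87 to about 0.92–0.98 and 0.83 to about 0.89–0.97. So 90% may be attainable. But those noise levels are assumptions of this review. The plan quantifies neither argument and derives no 90% figure from them. The gain also depends on combining regions within each patient. The plan's wording leaves open counting them separately, and entering them as separate rows in the Cox model gave a type I error of 25% and 17% in the same two settings instead of 5%. The plan does not specify that analysis, so this is a reason to clarify and not an error found.

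The 90% may also be 0.89 rounded up. That is the 2-year measurement-error cell, which is not labelled as adjusted.

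Noise from few runs is not excluded: at 200 runs per cell, pooling all three rows gives z = 1.35 (one-sided p = 0.09). Cells that imprecise would not support the sentence either.

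A fall is possible outside proportional hazards. When the effect was made to vanish after 2 years, adjusted power fell from 0.87 to 0.81, but unadjusted power fell further, from 0.76 to 0.63, unlike row 1. Only one such setting was tried, and it is not the stated model.

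Finally, the plan calls its data preliminary and concedes that funding limits accrual and power (sections 6.iii.4.d and 6.iii.14.c). That stands, and it limits the point to the stated figures.

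**Conclusion.** The concern holds and should be fixed. That 90% exceeds all six cells needs no assumption: the excess is 3 and 7 points for the planned adjusted analysis and 1 point for the highest cell. That rows 2 and 3 conflict with longer follow-up rests on the same patients, a constant hazard ratio and cells precise to two decimals. On that basis the 7-year cells imply 11% and 14% less information than the 2-year cells. Transposed headers or small-run noise may be the cause, and the documents do not settle which. The excess of row 3 over row 2 is a weaker sign, because the 15% error is undefined and the row's adjustment status is unknown. Whether true power lies above or below 90% cannot be determined. The point corrects reported figures and does not question the pilot or its size.

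**What to change.** - Check Table 6.iii.7 for transposed column headers and mislabelled rows.
- Recompute all six cells. State the scale of the 0.75 effect, alpha and sidedness, expected deaths at 2 and 7 years, the confounder assumptions, the measurement-error model, whether row 3 is adjusted, and the number of runs if the cells are simulated.
- Replace the 90% sentence with the recomputed power for the adjusted Cox analysis, naming the cell and the follow-up it refers to.
- If sub-regions are used, combine them into one measure per patient or use a variance clustered on patient. Do not count them as independent survival units.

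The cost is recalculation and wording. Enrolment, scans and visits do not change. The restated power may be higher or lower than the current cells.

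### Hypothesis 1 is planned with the 30% flux difference pointing against its own cited means; correcting the wording leaves the effect near 1.0, but that effect gives 73–87% power, not about 95%, and the t-test should be named as Welch's

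*Combined protocol and SAP*

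**What the plan says.** The Hypothesis 1 paragraph of section 6.iii.14.b compares mean FLT flux between true progression and pseudo-progression among GBM patients whose MRI suggests progression one month after treatment. It expects 40% of them to be pseudo-progressors. Its planning values come from earlier data on recurrence and radionecrosis: "KFLT recurrences showed a mean of 0.017 and a standard deviation of 0.005", and "The mean of the radionecrosis group was 0.004, roughly one-quarter for that for recurrences". No SD is given for radionecrosis.

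The paragraph then sets its alternative by "conservatively, assuming that pseudo-progressors showed even a 30% increase over the mean KFLT value", takes the difference as 0.017 × 0.3, or about 0.005, and concludes that "the expected standardized effect is 0.99". "Using a 2-sample t-test with significance level of 5% for assessment of the hypothesis", it puts power at about 95%. It does not say how many cases this assumes, whether the test is one- or two-sided, or whether the variances are pooled.

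The statistical section plans for 30 patients. Section 6.iii.4.d allows up to 40 to be enrolled, to offset an expected 25% with too few scans. Section 6.iii.3.a calls the distinction between progression and pseudo-progression the primary hypothesis.

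**The concern.** The two cited means put treatment effect at about a quarter of tumor. A cautious version of that contrast would shrink the gap but keep pseudo-progression lower. The sentence does the opposite: a 30% increase over 0.017 is 0.0221, above recurrence. It also fits poorly with the rationale in section 6.iii.3, where flux stands for proliferation.

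Since this is the planning alternative for the main question, three things need checking: whether the effect size survives a corrected direction, whether the stated power follows from it, and whether a single SD taken from one group is a sound basis for an unspecified t-test.

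**Working it through.** **Inputs.** All are from section 6.iii.14 unless noted: recurrence mean 0.017, SD 0.005; radionecrosis mean 0.004; relative difference 30%; significance level 5%; 60/40 split of true to pseudo-progression; N = 30, or 40 (section 6.iii.4.d). Assumed: two-sided test; equal SDs in steps 1–3.

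**Step 1: effect size.**
- As printed: 0.017 × 0.3 = 0.0051; 0.0051 / 0.005 = 1.02. With the rounded difference, 0.005 / 0.005 = 1.00.
- Direction corrected on the same base: pseudo mean 0.017 × 0.7 = 0.0119; difference 0.0051; effect 1.02. Nothing changes.
- The printed 0.99 needs an SD of 0.005 / 0.99 = 0.00505 to 0.0051 / 0.99 = 0.00515, both of which print as 0.005. If the mean lies in 0.0165–0.0175 and the SD in 0.0045–0.0055, the effect can be anywhere from 0.90 to 1.17. So 0.99 fits the plan's own inputs.

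**Step 2: power.** The noncentrality is d × √(n1·n2/(n1+n2)), with n1 + n2 − 2 degrees of freedom. For d = 0.99 and 18/12 this is 0.99 × √7.2 = 2.66 against a critical value of 2.05, giving 73%.

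| Cases (true/pseudo) | d = 0.99, two-sided | d = 1.02, two-sided | d = 0.99, one-sided | d = 1.02, one-sided |
|---|---|---|---|---|
| 18/12 (N = 30) | 73% | 75% | 83% | 85% |
| 24/16 (N = 40) | 85% | 87% | 91% | 93% |

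An even 20/20 split gives 86–88% two-sided and 92–94% one-sided. None of these reaches 95%. At a 60/40 split, 95% two-sided power needs 58 cases at d = 0.99 or 54 at d = 1.02. Thirty per group (60 in all) gives 96.5% at d = 0.99.

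**Step 3: who counts as a case.** The table uses every enrolled patient. The comparison is limited to GBM patients with apparent progression, while section 6.iii.4.a admits any primary, recurrent or metastatic brain tumor. Section 6.iii.3.a puts early MRI-defined failure in glioblastoma at 30–50%. Applied to 30 patients as an illustration, that leaves 9 to 15 cases (5/4 to 9/6), and power at d = 0.99 is 25–41%.

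**Step 4: pooled or Welch.** Simulation with difference 0.0051, true-progression SD 0.005 and normal data. The pseudo-progression SDs are assumptions; the plan gives none.

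| Cases | Pseudo SD | Type I error, pooled v Welch | Power, pooled v Welch |
|---|---|---|---|
| 18/12 | 0.0050 | 5.0% v 4.9% | 75% v 75% |
| 18/12 | 0.0035 | 3.7% v 4.8% | 86% v 89% |
| 18/12 | 0.0025 | 2.9% v 4.9% | 91% v 94% |
| 9/6 | 0.0050 | 5.0% v 4.8% | 43% v 41% |
| 9/6 | 0.0035 | 3.8% v 4.7% | 52% v 56% |
| 9/6 | 0.0025 | 3.2% v 4.8% | 58% v 66% |

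When the larger group is the more variable one, the pooled test is conservative. Unrounded, Welch's gain is 3.1–3.8 points at 18/12 and 4.5–8.7 at 9/6. With equal SDs it loses 0.7 points at 18/12 and 1.9 at 9/6.

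**The case against.** Several stronger readings are tempting, and the documents do not support them.

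- **That fixing the direction changes the effect size, or that 0.99 is wrong.** The inputs give 1.02 before and after the fix, 0.99 is within rounding, and two-sided power does not depend on sign. The wording error by itself costs no power.
- **That the true effect is 0.78.** This takes 30% of a pseudo-progressor mean: 0.017 / 1.3 = 0.0131, difference 0.0039, effect 0.78, power 53% (18/12) or 66% (24/16). But the plan prints its base as 0.017 × 0.3. The 0.78 is a sensitivity value for a different base, not a correction.
- **That the sentence reverses Hypothesis 1.** Hypothesis 1 in section 6.iii.3.c claims only a distinction, and 6.iii.14.b only a comparison of means. Neither states a direction. The conflict is with the cited means.
- **That the plan commits to a pooled test.** It says only a two-sample t-test, which does not exclude Welch. Using 0.005 for both groups is, if anything, cautious for planning: in step 4, a smaller pseudo-progression SD raises power under either test.

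It is also fair to say that the intended direction can be recovered, that 30% is modest beside the fourfold contrast cited, and that this is a pilot which admits limited power in sections 6.iii.4.d and 6.iii.14.c. At the full cited contrast, (0.017 − 0.004) / 0.005 = 2.6, power would be 91% even at 5/4. This limits the practical harm. It does not rescue a power figure that the plan ties to an effect of 0.99.

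**Conclusion.** The concern holds in three limited parts. First, the planning sentence contradicts the means it cites and needs rewording, with no effect on the difference of 0.0051 or the effect of about 1.0. Second, that effect does not give the stated power: 73–75% with 30 analysable cases and 85–87% with 40, two-sided, and at most 94% one-sided. These figures rest on equal SDs and on every enrolled patient being a GBM patient with apparent progression, which is the most favourable case. Third, the t-test should be specified. The advantage of Welch depends on pseudo-progressors being less variable, which is plausible for a positive rate constant with a lower mean but is not shown in the documents.

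**What to change.** In section 6.iii.14.b:

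1. State that pseudo-progressors are assumed to be 30% lower than the recurrence mean (about 0.012 v 0.017). The effect of 0.99 can stay. If the authors meant a different base, they should say so and use the effect it gives.
2. Replace the 95% figure with power at a stated number of cases and sidedness: 73–75% for 18/12 and 85–87% for 24/16, two-sided. Add the number of GBM patients with apparent progression that is realistically expected, and the power at that number.
3. Name Welch's t-test, or an analysis of log KFLT, for Hypothesis 1. Report the radionecrosis SD if the investigators have it.

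The cost is a few sentences and no change to trial procedures. If the SDs prove equal, Welch gives up about 1–2 points of power.
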